- Moderate : I noticed the symptom. It bothered me enough that I didn't do as much as I usually do.
- Severe : I really noticed the symptom. It kept me from doing something I wanted or had to do.

Participant Diary HPV-301 Version 1.0 - 10 May 2016

Day 4: 4 Days After Injec	tion Subject#	! :	Date:		
The items on this page refer to the information changes after you fill	e time between midn out this page but befo	ight of last night an o re 11:59 p.m. tonigh	d 11:59 p.m. today nt, make any necess	(Day 4). If sary changes b	any of the selow.
Temperature					
Evening Temp.: °C	or °F (circle one)	Time Taken:	AM c	or PM (circle o	one)
General Symptoms If you experience any of these syn (Day 4). See General Instruction	s on page 10 for more	that describes your e information.		til 11:59 p.m.	tonight
Symptom	None	Mild	Moderate	_	ere
Unusually tired/feeling unwell					
Muscle aches					
Headache					
Nausea					
Joint pain					
If you experience an injection site (Day 4). See General Instruction Symptom			ur worst symptom Moderate		m. tonight
Pain					
Itching					
Telling	_				- 0
Redness, Swelling, or Bruising	None	Provid	e Maximum Meas	urement	
Redness		Constitution (Constitution Constitution Cons	cm at the longes		
Swelling		cm at the longest part			
Bruising			cm at the longes		
Other Symptoms If you experience symptoms other Instructions on page 10. Did you experience any other			ace below accordin	ng to the Gene	eral
Sympt	om or Medical Evo	ent	Mild	Moderate	Severe
Did you take any medications If yes, please list out the name		pelow:			

Participant Diary HPV-301 Version 1.0 - 10 May 2016

Temperature

Take your temperature orally around the same time each evening, using the thermometer provided and record it in the space provided. Also record the time at which you took your temperature. If you recently drank very hot or cold liquids, wait 15 minutes before taking your temperature.

Injection Site Symptoms

Pain and itching

Some people experience pain in the area where they were injected. Some people may also experience itching in the area where they were injected.

• By pain we mean that the place where you were injected hurts even when it isn't touched.

If you experience pain or itching at the injection site, use the following categories to describe how severe these symptoms were. If you don't experience one or more of these symptoms, mark the **NONE** box.

- Moderate I noticed the discomfort and didn't use my arm as much as usual.
- Severe ! I really noticed the discomfort. It kept me from doing something I wanted or had to do.

Redness, swelling, and bruising

Some people experience redness, swelling, or bruising in the area where they were injected. If you experience redness, swelling, or bruising, measure the area using the measuring tool you were provided, and record the measurement in the space provided.

To measure the area of redness, swelling, or bruising, do the following:

[figure not shown]
- Place the measuring tool over the area where you were injected, with the dot over the center of the area.
- Select the circle where the longest part of the area touches the line.
- If the area is in between two circles, select the larger circle

For example, the area shown to the right measures 3 centimeters (cm) because it is touching the 3cm line.

General and Other Symptoms or Medications

If you have additional symptoms that are not listed, or if you sought medical care for any reason from a health care provider (e.g. doctor's office, emergency room), or if you took any medications, these should be listed in the spaces provided. Please designate any symptoms as Mild, Moderate, or Severe.

- Mild i I only had minor discomfort. I went about my usual activities.
- Moderate : I noticed the symptom. It bothered me enough that I didn't do as much as I usually do.
- Severe I really noticed the symptom. It kept me from doing something I wanted or had to do.

Day 5: 5 Days After Inje	ection Subject #:		Date: _		
The items on this page refer to information changes after you fi					
Temperature					
	C or °F (circle one)	Time Taken:	AM	or PM (circle o	one)
General Symptoms If you experience any of these sy (Day 5). See General Instructi	ons on page 12 for mor	e information.			
Symptom	None	Mild	Moderate		vere
Unusually tired/feeling unwell				-	
Muscle aches					
Headache					
Nausea					
Joint pain					
Symptom Pain Itching	None □	Mild	Moderate		vere
Redness, Swelling, or Bruising	g None	Duovid	Maximum Mea	auuam ant	
Redness Redness		rrovia	cm at the longe		
1 1 1 1 1 1 1 1 1 1 1 1 1 1 1 1 1 1 1	+ + +		cm at the longe		
Swelling Bruising			cm at the longe		
Other Symptoms If you experience symptoms oth Instructions on page 12. Did you experience any other			ace below accord	ing to the Gene	eral
Sym	ptom or Medical Eve	ent	Mild	Moderate	Severe
•		and a second			
Did you take any medication If yes, please list out the nan		elow:			

Participant Diary HPV-301 Version 1.0 - 10 May 2016

Temperature

Take your temperature orally around the same time each evening, using the thermometer provided and record it in the space provided. Also record the time at which you took your temperature. If you recently drank very hot or cold liquids, wait 15 minutes before taking your temperature.

Injection Site Symptoms

Pain and itching

Some people experience pain in the area where they were injected. Some people may also experience itching in the area where they were injected.

• By pain we mean that the place where you were injected hurts even when it isn't touched.

If you experience pain or itching at the injection site, use the following categories to describe how severe these symptoms were. If you don't experience one or more of these symptoms, mark the **NONE** box.

- Mild in I only had a little discomfort. I could still use my arm like always.
- Moderate ! I noticed the discomfort and didn't use my arm as much as usual.
- Severe I really noticed the discomfort. It kept me from doing something I wanted or had to do.

Redness, swelling, and bruising

Some people experience redness, swelling, or bruising in the area where they were injected. If you experience redness, swelling, or bruising, measure the area using the measuring tool you were provided, and record the measurement in the space provided.

To measure the area of redness, swelling, or bruising, do the following:

- Place the measuring tool over the area where you were injected, with the dot over the center of the area.
- Select the circle where the longest part of the area touches the line.
- If the area is in between two circles, select the larger circle.

For example, the area shown to the right measures 3 centimeters (cm) because it is touching the 3cm line.

General and Other Symptoms or Medications

If you have additional symptoms that are not listed, or if you sought medical care for any reason from a health care provider (e.g. doctor's office, emergency room), or if you took any medications, these should be listed in the spaces provided. Please designate any symptoms as Mild, Moderate, or Severe.

- Mild I only had minor discomfort. I went about my usual activities.
- Moderate . I noticed the symptom. It bothered me enough that I didn't do as much as I usually do.
- Severe I really noticed the symptom. It kept me from doing something I wanted or had to do.

Day 6: 6 Days After In				//	
The items on this page refer to symptoms you reported on pre or Doctor know. Temperature					
Evening Temp.:	°C or °F (circle one)	Time Taken:	AM c	or PM (circle o	one)
General Symptoms If you experience any of these (Day 6). See General Instruc			worst symptom un	til 11:59 p.m.	tonight
Symptom	None	Mild	Moderate		ere
Unusually tired/feeling unwe					
Muscle aches				_	
Headache					
Nausea					
Joint pain					
Injection Site Symptoms If you experience an injection (Day 6). See General Instruc	ctions on page 14 for mo	re information.			2153
Symptom	None	Mild	Moderate	_	ere
Pain					
Itching					
D 1 6 W D 1		75			
Redness, Swelling, or Bruisi Redness	ng None	Provide	e Maximum Meas		
Swelling		(7	cm at the longest		
Bruising			cm at the longes		
Bruising			chi at the longes	ı parı	
Other Symptoms If you experience symptoms o Instructions on page 14. Did you experience any ot		 	ace below according	ng to the Gene	eral
Syı	nptom or Medical Ev	ent	Mild	Moderate	Severe
Did you take any medicati If yes, please list out the na		below:			

Participant Diary HPV-301 Version 1.0 - 10 May 2016

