
4.0

Day 2: 2 Days After Injec	ction Sub	oject #:	Date:	//	'	
The items on this page refer to the time between midnight of last night and 11:59 p.m. today (Day 2). If any of th information changes after you fill out this page but before 11:59 p.m. tonight, make any necessary changes below.						
Temperature						
Evening Temp.: °C o	or °F (circle one)	Time Taken:	AM o	or PM (circle o	one)	
General Symptoms If you experience any of these sym (Day 2). See General Instruction	s on page 6 for mo	ox that describes your re information.	worst symptom un			
Symptom Unusually tired/feeling unwell	None	Mild	Moderate		ere	
Muscle aches				200		
	1,	107-10				
Headache						
Nausea			 			
Joint pain						
Injection Site Symptoms If you experience an injection site (Day 2). See General Instruction	s on page 6 for mo	re information.	87 % 8E		1077	
Symptom	None	Mild	Moderate		ere	
Pain						
Itching						
Redness, Swelling, or Bruising	None	Provid	e Maximum Meas	urement		
Redness		 	cm at the longest	t part		
Swelling			cm at the longest	t part		
Bruising			cm at the longest	t part		
Other Symptoms If you experience symptoms other Instructions on page 6. Did you experience any other	59 00 N	-	ace below according	ng to the Gene	eral	
Sympto	om or Medical E	vent	Mild	Moderate	Severe	
			- -			
Did you take any medications If yes, please list out the name						

Temperature

Take your temperature orally around the same time each evening, using the thermometer provided and record it in the space provided. Also record the time at which you took your temperature. If you recently drank very hot or cold liquids, wait 15 minutes before taking your temperature.

Injection Site Symptoms

Pain and itching

Some people experience pain in the area where they were injected. Some people may also experience itching in the area where they were injected.

By pain we mean that the place where you were injected hurts even when it isn't touched.

If you experience pain or itching at the injection site, use the following categories to describe how severe these symptoms were. If you don't experience one or more of these symptoms, mark the NONE box.

- Mild in I only had a little discomfort. I could still use my arm like always.
- Moderate I noticed the discomfort and didn't use my arm as much as usual.
- Severe ... I really noticed the discomfort. It kept me from doing something I wanted or had to do.

Redness, swelling, and bruising

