The items on this page refer to the time between midnight of last night and 11:59 p.m. today (Day 6). If any of the symptoms you reported on previous pages have not gone away ("resolved"), you will need to let the Site Coordinator or Doctor know. Temperature							
Evening Temp.: °C or °F (circle one) Time Taken:AM or PM (circle one)							
General Symptoms If you experience any of these symptoms, mark the box that describes your worst symptom until 11:59 p.m. tonight (Day 6). See General Instructions on page 14 for more information.							
Symptom	None	Mild	Moderate		ere		
Unusually tired/feeling unwell							
Muscle aches]		
Headache							
Nausea							
Joint pain							
If you experience an injection site (Day 6). See General Instruction	Injection Site Symptoms If you experience an injection site symptom, mark the box that describes your worst symptom until 11:59 p.m. tonight (Day 6). See General Instructions on page 14 for more information.						
Symptom	None	Mild	Moderate		ere		
Pain							
Itching							
Redness, Swelling, or Bruising	None	Provide	Maximum Meas	urement			
Redness		100	cm at the longes				
Swelling			cm at the longes				
Bruising			cm at the longes				
Other Symptoms If you experience symptoms other than the ones above, write them in the space below according to the General Instructions on page 14. Did you experience any other symptoms? Yes No							
Symp	tom or Medical Eve	ent	Mild	Moderate	Severe		
Did you take any medications?							
25							

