6.3.3.10 Subject Post Treatment Assessments

PDC will capture subject reported local and systemic events for 7 days after the study treatment as shown in Appendix A.

The subject will be provided a PDC and will be asked to record the following the evening of study treatment through Day 6:

- Oral temperature and time taken (before 11:59 pm)
- General symptoms of feeling unwell
- Pain and itching at injection site
- Measure redness, swelling, bruising at injection site
- Medications taken

The completed PDC will be reviewed with the subject and research staff at 8 -14 Days post-dose.

The study staff will review the PDC for general symptoms (e.g. malaise, fatigue, headache, nausea, and myalgia/arthralgia), injection site reaction symptoms (e.g. pain, erythema and edema), medical events and medications. All reported events will be assessed for clinical significance (CS) and reported as adverse event accordingly.

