7.3.1 EVENTS REQUIRING EXPEDITED REPORTING

Events requiring expedited reporting (ERER) will be defined as related adverse events due to VGX-3100X/placebo delivered with CELLECTRA[™] 5PSP that meets any of the following criteria:

- Grade 3 or greater administration site erythema, and/or induration recorded ≥ 2 hours after Study Treatment
- Grade 4 or greater administration site pain, tenderness recorded ≥ 2 hours after Study Treatment
- Grade 3 or greater fever
- Grade 3 or greater systemic symptoms, including generalized pruritus

As per the Toxicity Grade for Healthy Adults and per CTCAE v 4.03. The most severe grade for that particular event is to be documented in the CRFs.

Sites will inform the Sponsor vial email and to designee vial phone or fax of any ERER within 24 hours to discuss whether further dosing should continue by contacting Inovio as follows.

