7.3.2 STOPPING RULES (CRITERIA FOR PAUSING OF STUDY)

- If at any time during a study one-third (1/3) or more of the subjects experience an ERER, further enrollment and study treatment will be halted immediately until a thorough investigation has been conducted by the Medical Monitor, Principal Investigator for the trial, and the DSMB. Only the DSMB may review unblinded data in making their recommendation to the Sponsor regarding continuation of a trial.
- If any SAE (or potentially life-threatening AE), or death assessed as related to study treatment occurs, further enrollment and study treatment will be halted immediately until a thorough investigation has been conducted by the Medical Monitor, Principal Investigator for the trial, IRB (if applicable) and the DSMB.
- If three or more subjects in this study, experience the same Grade 3 or 4 adverse event, assessed as related to study treatment, further enrollment and study treatment will be halted immediately until a thorough investigation has been conducted by the Medical Monitor, Principal Investigator for the trial, and the DSMB.
- In the event of two identical, unexpected, Grade 4 toxicities, assessed as related to study treatment, further enrollment and study treatment will be halted immediately until a thorough investigation has been conducted by the Medical Monitor, Principal Investigator for the trial, IRB (if applicable) and the DSMB.

The sponsor or designee will notify all investigators and IRBs/EC (if required) regarding the outcome of any investigation stemming from a Study Pause.

Guidelines for assessing relatedness are detailed in Section 7.1.6.

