15 APPENDICES

15.1 APPENDIX A: PARTICIPANT DIARY CARD

Subject Diary

HPV-301

Subject #: _	
Injection Da	ate:

Note to Participant:For questions or problems, please contact your Site Coordinator.

Name:	
Telephone: ()
Email (optional):	

Participant Diary HPV-301 Version 1.0 - 10 May 2016

Temperature

Take your temperature orally around the same time each evening, using the thermometer provided and record it in the space provided. Also record the time at which you took your temperature. If you recently drank very hot or cold liquids, wait 15 minutes before taking your temperature.

Injection Site Symptoms

Pain and itching

Some people experience pain in the area where they were injected. Some people may also experience itching in the area where they were injected.

• By pain we mean that the place where you were injected hurts even when it isn't touched.

If you experience pain or itching at the injection site, use the following categories to describe how severe these symptoms were. If you don't experience one or more of these symptoms, mark the **NONE** box.

- Mild in I only had a little discomfort. I could still use my arm like always.
- Moderate . I noticed the discomfort and didn't use my arm as much as usual.
- Severe I really noticed the discomfort. It kept me from doing something I wanted or had to do.

Redness, swelling, and bruising

Some people experience redness, swelling, or bruising in the area where they were injected. If you experience redness, swelling, or bruising, measure the area using the measuring tool you were provided, and record the measurement in the space provided.

To measure the area of redness, swelling, or bruising, do the following:

- Place the measuring tool over the area where you were injected, with the dot over the center of the area.
- Select the circle where the longest part of the area touches the line.
- If the area is in between two circles, select the larger circle.

For example, the area shown to the right measures 3 centimeters (cm) because it is touching the 3cm line.

General and Other Symptoms or Medications

If you have additional symptoms that are not listed, or if you sought medical care for any reason from a health care provider (e.g. doctor's office, emergency room), or if you took any medications, these should be listed in the spaces provided. Please designate any symptoms as Mild, Moderate, or Severe.

- Mild I only had minor discomfort. I went about my usual activities.

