- Moderate : I noticed the symptom. It bothered me enough that I didn't do as much as I usually do.
- Severe I really noticed the symptom. It kept me from doing something I wanted or had to do.

Day 0: Evening of Injection	on Subject#:		Date:	//	
Sometime during the evening on the refer to the time from your injection after you fill out this page but before the source of t	n to 11:59 p.m. on the	e day of injection (D	ay 0). If any of th	e items on this e information	s page changes
Temperature					
-	or °F (circle one)	Time Taken:	AM c	or PM (circle o	one)
General Symptoms If you experience any of these symtonight (Day 0). See General Inst	tructions on page 2 fo	that describes your or more information.	worst the symptom		
Symptom	None	Mild	Moderate	0.000	ere
Unusually tired/feeling unwell				_	
Muscle aches					
Headache					
Nausea					
Joint pain					
(Day 0). See General Instruction Symptom	None	Mild	Moderate		/ere
Pain					
Itching					
Redness, Swelling, or Bruising Redness	None 🗆	Provide Maximum Measurement cm at the longest part			
Swelling			cm at the longest		
Bruising			cm at the longest		
Other Symptoms If you experience symptoms other Instructions on page 2. Did you experience any other			ace below according	ig to the Gene	eral
Symnt	om or Medical Eve	ent	Mild	Moderate	Severe
Зушро	om of Medical Eve	int .			
					-
Did you take any medications If yes, please list out the name	100 VICTOR	pelow:			
-					
Participant Diary HPV-301 Version 1.0 - 10 May 2016					Page 3

203

Temperature

Take your temperature orally around the same time each evening, using the thermometer provided and record it in the space provided. Also record the time at which you took your temperature. If you recently drank very hot or cold liquids, wait 15 minutes before taking your temperature.

Injection Site Symptoms

Pain and itching

Some people experience pain in the area where they were injected. Some people may also experience itching in the area where they were injected.

• By pain we mean that the place where you were injected hurts even when it isn't touched.

If you experience pain or itching at the injection site, use the following categories to describe how severe these symptoms were. If you don't experience one or more of these symptoms, mark the **NONE** box.

- Moderate I noticed the discomfort and didn't use my arm as much as usual.
- Severe I really noticed the discomfort. It kept me from doing something I wanted or had to do.

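### The diary takes one evening temperature but the day's worst or maximum for every other graded or measured item, so peak fever may be under-recorded

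*Protocol*

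**What the plan says.** The diary in Appendix A (section 15.1) has the participant take an oral temperature at much the same hour every evening and then "record it in the space provided. Also record the time at which you took your temperature". Each daily page has one temperature field and one clock time. Section 6.3.3.10 lists the same item, "Oral temperature and time taken (before 11:59 pm", from the evening of treatment through Day 6.

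The other items on the same page follow a different rule. For the listed general symptoms and for pain and itching the instruction is to "mark the box that describes your worst symptom until 11:59 p.m. tonight (Day 6", with matching wording on the other days. For redness, swelling and bruising the page says "Provide Maximum Measurement".

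Section 7.3.1 lists "Grade 3 or greater fever" among the related events that need expedited reporting, graded "As per the Toxicity Grade for Healthy Adults and per CTCAE v 4.03". Section 7.3.2 pauses enrolment and treatment "If three or more subjects in this study, experience the same Grade 3 or 4 adverse event" that is judged related to study treatment.

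The file holds this diary twice, as a Subject Diary Card and as a Participant Diary Card. Both carry the same diary version number and date. The later copy and the 7.3.1 text belong to protocol version 2.1.

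**The concern.** Temperature is the only graded or measured item on the page without a worst-of-day or maximum rule. Fever is also absent from the symptom checklist, which covers tiredness or feeling unwell, muscle aches, headache, nausea and joint pain. The evening reading is thus the only prompted fever item.

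The rest of the plan works with maxima. Section 7.1.5 records each adverse event at its greatest severity, 7.3.1 wants the most severe grade in the CRF, and 8.11.1 counts repeated events on a worst-case basis. For fever, the diary does not ask for the value these rules need.

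Two things are at stake. The first is the incidence and severity of fever as a systemic event in secondary endpoint 1a. The second is the sensitivity of the Grade 3 fever criterion and of the pause rule that a related Grade 3 fever can feed.

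**Working it through.** The protocol states no fever rate, fever duration or capture rate, so there is no figure to reproduce. The check is a comparison of wording, followed by an illustration under stated assumptions.

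**Wording, item by item (Appendix A)**

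- General symptoms: worst of the day.
- Pain and itching: worst of the day.
- Redness, swelling, bruising: maximum of the day.
- Temperature: one evening reading with its time, which is 7 readings per dose and 7 × 3 = 21 over three doses.
- Other symptoms and medications: open lists with no worst or maximum rule, so the contrast covers graded and measured items only.

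**Could another route supply a gradable temperature?**

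- Amending the page: the diary says that if "information changes after you fill out this page but before 11:59 p.m. tonight, make any necessary changes below". This permits a correction, but nothing prompts a second reading.
- Free-text symptoms: rated mild, moderate or severe by effect on activities, which yields no temperature.
- Immediate reporting of events (6.6) and questioning at visits (7.2): these can establish that a fever occurred. The diary review comes 8 to 14 days after the dose, when a temperature that was not taken cannot be recovered.

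The protocol text shown prints no temperature cut-offs for fever grades. The reasoning takes it that a fever grade is set by a measured temperature.

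**Illustration 1: one reading against one fever.** Assume a single fever of L hours, onset uniform over the day, and the evening reading as the only source. The chance that the reading falls inside the fever is min(1, L/24):

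| L (hours) | L/24 | Chance |
|---|---|---|
| 4 | 4/24 | 17% |
| 6 | 6/24 | 25% |
| 8 | 8/24 | 33% |
| 12 | 12/24 | 50% |
| 18 | 18/24 | 75% |
| 24 or more | capped at 1 | 100% |

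Even when the reading falls inside the fever, it need not be the peak.

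**Illustration 2: the three-subject rule.** Let q = true rate of related Grade 3 fever × proportion captured. The chance of at least three recorded cases among N subjects is 1 − Σ C(N,k) q^k (1−q)^(N−k), summed over k = 0, 1, 2. N is 198 in version 3.0 and 165 in version 2.1. The rates and capture proportions are assumed.

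| N, true rate | Capture 100% | 75% | 50% | 25% |
|---|---|---|---|---|
| 198, 2% | 0.76 | 0.57 | 0.32 | 0.08 |
| 165, 2% | 0.64 | 0.45 | 0.23 | 0.05 |
| 198, 5% | 0.997 | 0.98 | 0.87 | 0.45 |

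The rule can lose sensitivity, but how much depends entirely on the assumed inputs.

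**The case against.** A reader might infer that fevers at other times of day are missed and that the Grade 3 criterion often cannot be evaluated. The documents do not support this. An evening value can be graded, other reporting routes exist, the participant holds the thermometer, and no rate or duration is given from which to say how often.

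A reader might also point to the rule that pauses the study when one third of subjects have an event requiring expedited reporting. That consequence is weak. One third is 165/3 = 55 subjects in version 2.1, counting events of any listed type. Fever is not among the common or significantly increased events of the Phase 2b summary in 2.3, nor is it named in Table 11, where the nearest entry is chills and flu-like syndrome under unknown or theoretical risks. Only the three-subject rule is plausibly sensitive.

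Three further objections have force. Uniform onset is doubtful, since a fever caused by an injection would follow the injection in time, and Day 0 already has a reading that evening. The analgesics offered under 6.4.2 could lower any later reading, including a day's highest, so the point does not rest on them. A fixed-time reading is standardised, whereas extra readings depend on feeling feverish. Blinding may not fully equalise that: erythema in Phase 2b was 78% on active against 57% on placebo. This argues for keeping the evening reading and reporting it separately. It is no worse a limitation than that of the worst-of-day items already collected.

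Finally, version 3.0 renamed the 7.3.1 list as adverse events of special interest, and neither that section nor its diary is shown. Its summary of changes mentions no change to the diary or to temperature, so carry-over is plausible but unproven.

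**Conclusion.** The point holds as a limited weakness in data collection. In the diary shown, a fever outside the evening reading has no prompted measured value, while every other graded or measured solicited item is taken at its worst or maximum. Peak fever may therefore be under-recorded for endpoint 1a, and the Grade 3 fever criterion and the three-subject pause rule may be under-detected. This is a mismatch between the temperature item and its uses, not a contradiction in the text.

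The size of the loss is unknown. The figures above rest on assumed durations, rates, capture and uniform onset, and serve only to show the direction. The conclusion applies to version 2.1, and to version 3.0 only if the wording carried over. It is a low-severity point that is worth making because the remedy is cheap.

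**What to change.** First confirm whether the version 3.0 diary and the renamed 7.3.1 section keep the single evening reading and the fever criterion. If they do:

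- Keep the fixed evening reading as it is.
- Add one line to each diary day: if you felt feverish at any other time, take your temperature, and write down the highest temperature taken today and its time. Add the matching CRF field.
- Derive fever incidence and grade from the day's highest value, counting the evening reading among the candidates.
- Report the evening reading separately by arm, as the standardised measure.

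The cost is one diary line per day, one CRF field and a small change to the derivation. The thermometer is already supplied. The drawback is that the additional readings are prompted by symptoms, which the separate evening summary makes visible. No change to the fever criterion or to the pause rules is proposed.
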